5.8 Subject Withdrawal/Discontinuation Criteria

Subjects may withdraw consent at any time for any reason or be dropped from the trial at the discretion of the investigator should any untoward effect occur. In addition, a subject may be withdrawn by the investigator or the Sponsor if enrollment into the trial is inappropriate, the trial plan is violated, or for administrative and/or other safety reasons. Specific details regarding discontinuation or withdrawal procedures; including specific details regarding withdrawal from Future Biomedical Research, are provided in Section 7.1.4 – Other Procedures.

A subject must be discontinued from the trial for any of the following reasons:

- The subject or legal representative (such as a parent or legal guardian) withdraws consent.

A subject must be discontinued from treatment (but may continue to be monitored in the trial) for any of the following reasons:

- The subject or legal representative (such as a parent or legal guardian) withdraws consent for treatment but agrees to continue to participate in the regularly scheduled study activities.
- Documented disease progression as assessed by the investigator. (2 consecutive assessments are needed for disease progression. Clinical deterioration will not be considered progression). Note: Subjects with documented disease progression may continue to receive trial treatment, at the discretion of the study investigator prior consultation with the Sponsor, if they meet the criteria outlined in Section 7.1.2.8.6

- Unacceptable adverse experiences as described in Sections 5.2.1.2, and 5.6.1.
- Intercurrent illness that prevents further administration of treatment.
- The subject has a confirmed positive serum pregnancy test.
- Subjects who receive any non-protocol specified anti-myeloma therapy prior to documented progression will be discontinued from all study treatment (including pomalidomide and low dose dexamethasone); however, tumor assessments must continue at 4 week intervals until documented progression.
- Noncompliance with trial treatment or procedure requirements.
 - Subjects experiencing a > 12 weeks delay between pembrolizumab doses in the investigational arm (Arm A) or > 28 day delay for both pomalidomide and low dose dexamethasone in the control arm (Arm B) due to an adverse event(s) related to study treatment must be discontinued from treatment.

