 - Subjects experiencing >28 days delays in all study drugs due medical/surgical events or logistical reasons unrelated to study therapy must be discontinued from treatment.

NOTE: For both groups, if either pembrolizumab, pomalidomide, or low dose dexamethasone is discontinued due to unacceptable toxicity, subjects can continue to receive study treatment with the remaining study drugs without discontinuing from study.

- The subject is lost to follow-up.
- Administrative reasons.

The End of Treatment and Follow-up Visit procedures are listed in Section 6 (Flow Chart) and Section 7.1.5 (Visit Requirements). After the end of treatment, each subject will be followed for 30 days for AE monitoring (SAEs will be collected for 90 days after the end of treatment as described in Section 7.2.3.1). Subjects who discontinue for reasons other than progressive disease will have post-treatment follow-up for disease status until disease progression, initiating a non-study cancer treatment, withdrawing consent or becoming lost to follow-up. Prior to discontinuing patients from therapy, consult with Sponsor and submit the Treatment Termination & Disease Assessment Termination Form. After documented disease progression or the start of new antineoplastic therapy each subject will be followed for overall survival until death, withdrawal of consent, or the end of the study, whichever occurs first.

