8.4 Analysis Endpoints

8.4.1 Efficacy Endpoints

Primary

Progression-free survival (PFS) – the International Myeloma Working Group response criteria (IMWG 2011) by CAC blinded **central review**

PFS is defined as the time from randomization to the first documented disease progression per IMWG 2011 based on CAC blinded central review or death due to any cause, whichever occurs first. See Section 8.6.1 for definition of censoring.

Overall Survival (OS)

OS is defined as the time from randomization to death due to any cause. Subjects without documented death at the time of the final analysis will be censored at the date of the last follow-up.

Secondary

Overall Response Rate (ORR) – the International Myeloma Working Group response criteria (IMWG 2011) by CAC **blinded central review**.

ORR is defined as the proportion of the subjects in the analysis population who achieved at least a partial response according to the IMWG 2011.

Duration of Response (DOR) – the International Myeloma Working Group response criteria (IMWG 2011) by CAC **blinded central review**.

For subjects who demonstrated at least a partial response, response duration is defined as the time from first documented evidence of at least a partial response until disease progression or death. Response duration for subjects who have not progressed or died at the time of analysis will be censored at the date of their last assessment.

Disease Control Rate (DCR) - the International Myeloma Working Group response criteria (IMWG 2011) by CAC **blinded central review**.

Disease control rate (DCR) is defined as the percentage of subjects who have achieved confirmed CR, VGPR, PR, MR or have demonstrated SD for at least 12 weeks prior to any evidence of progression.

Second Progression-Free Survival (PFS2) - the time from randomization to subsequent disease progression after initiation of new anti-cancer therapy, or death from any cause, whichever occurs first, **based on Investigator assessment**.

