8.6 STATISTICAL METHODS

8.6.1 Statistical Methods for Efficacy Analyses

This section describes the statistical methods that address the primary and secondary objectives. Methods related to exploratory objectives and exploratory endpoints will be described in the supplemental statistical analysis plan (sSAP), this includes the ePRO data described in 7.1.2.9. In addition, a separate SAP will describe the analysis of Pharmacokinetic (PK) data described in Section 7.1.3.2

Efficacy results that will be deemed to be statistically significant after consideration of the Type I error control strategy are described in Section 8.8, Multiplicity and Section 8.7 Interim Analysis. Nominal p-values will be provided for other efficacy analyses, but should be interpreted with caution due to potential issues of multiplicity.

Progression-free Survival (PFS)

The non-parametric Kaplan-Meier method will be used to estimate the PFS curve in each treatment group. The treatment difference in PFS will be assessed by the stratified log-rank test. A stratified Cox proportional hazards model with Efron's method of tie handling will be used to assess the magnitude of the treatment difference (ie, hazard ratio) between the treatment arms. The hazard ratio and its 95% confidence interval from the stratified Cox model with Efron's method of tie handling and with a single treatment covariate will be reported. Disease status and number of previous treatments will be used as the stratification factors in both the stratified log-rank test and the stratified Cox model.

Since disease progression is assessed periodically, PD can occur any time in the time interval between the last assessment where PD was not documented and the assessment when PD is documented. For the primary analysis, for the subjects who have PD, the true date of disease progression will be approximated by the date of the first assessment at which PD is objectively documented per IMWG 2011, regardless of discontinuation of study drug. Death is always considered as a confirmed PD event. Subjects without documented PD/death will be censored at the last disease assessment date.

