In order to evaluate the robustness of the primary endpoint PFS per IMWG 2011 criteria by CAC blinded central review, two sensitivity analyses will be performed with a different set of censoring rules. The first sensitivity analysis is the same as the primary analysis except that it censors at the last disease assessment without PD when PD or death is documented after more than one missed disease assessment. The second sensitivity analysis is the same as the primary analysis except that it considers discontinuation of treatment or initiation of an anticancer treatment subsequent to discontinuation of study-specified treatments, whichever occurs later, to be a PD event for subjects without documented PD or death. The censoring rules for primary and sensitivity analyses are summarized in [Table 14](#) below. In case there is an imbalance between the treatment groups on disease assessment schedules or censoring patterns, additional PFS sensitivity analyses may be performed: 1. A PFS analysis using time to scheduled disease assessment visit from randomization as opposed to actual disease assessment time and 2) Finkelstein (1986)'s likelihood-based score test [55] for interval-censored data, which modifies the Cox proportional hazards model for interval censored data, will be used as a supportive analysis for the PFS endpoint. The interval will be constructed so

that the left endpoint is the date of the last disease assessment without documented PD and the right endpoint is the date of documented PD or death, whichever occurs earlier.

Table 14 Censoring rules for Primary and Sensitivity Analyses of PFS

Situation	Primary Analysis	Sensitivity Analysis 1	Sensitivity Analysis 2
No PD and no death; new anticancer treatment is not initiated	Censored at last disease assessment	Censored at last disease assessment	Censored at last disease assessment if still on study therapy; progressed at treatment discontinuation otherwise
No PD and no death; new anticancer treatment is initiated	Censored at last disease assessment before new anticancer treatment	Censored at last disease assessment before new anticancer treatment	Progressed at date of new anticancer treatment
PD or death documented after ≤ 1 missed disease assessment	Progressed at date of documented PD or death	Progressed at date of documented PD or death	Progressed at date of documented PD or death

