PD or death documented after ≥ 2 missed disease assessments	Progressed at date of documented PD or death	Censored at last disease assessment prior to the ≥ 2 missed disease assessment	Progressed at date of documented PD or death

The proportional hazards assumption of the Cox model will be examined using both graphical and analytical methods for the PFS analysis. The log[-log] of the survival function vs. time for PFS will be plotted for each treatment arm. If the curves are not parallel, indicating that hazards are not proportional, supportive analyses may be conducted to account for the possible non-proportional hazards effect associated with immunotherapies, for example, using Restricted Mean Survival Time (RMST) method [56], parametric method [57] etc. Details will be described in supplemental SAP.

Overall Survival (OS)

The non-parametric Kaplan-Meier method will be used to estimate the survival curves. The treatment difference in survival will be assessed by the stratified log-rank test. A stratified Cox proportional hazards model with Efron's method of tie handling will be used to assess the magnitude of the treatment difference (ie, the hazard ratio). The hazard ratio and its 95% confidence interval from the stratified Cox model with a single treatment covariate will be reported. Disease status and number of prior treatments will be used as the stratification factors in both the stratified log-rank test and the stratified Cox model.

Exploratory analyses to adjust for the effect of subsequent lines of therapy on OS may be performed based on recognized methods, eg, the Rank Preserving Structural Failure Time (RPSFT) model proposed by Robins and Tsiatis (1989) [58], two stage model, etc. The choice of the method will be based on an examination of the appropriateness of the data to the assumptions required by the method. Other sensitivity analyses described for the PFS endpoint will be applied to OS endpoint as appropriate. Further details of sensitivity analyses will be described in supplemental SAP.

Overall Response Rate (ORR)

The stratified Miettinen and Nurminen's method based on sample size weighting will be used for comparison of the ORR between the treatment groups. A 95% confidence interval for the difference in response rates between the active arms and the standard therapy arm will be provided. Disease status and number of prior treatments will be used as the stratification factors in the analysis.

Duration of Response (DOR)

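### Table 14's primary PFS censoring of subjects who start new therapy without progression depends on what happens to them afterwards

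*Combined protocol and SAP*

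**What the plan says.** Section 8.4.1 runs primary PFS from randomization to the first progression (PD) on blinded central review "or death due to any cause, whichever occurs first. See Section 8.6.1 for definition of censoring".

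The PFS text of section 8.6.1 adds two rules: "Death is always considered as a confirmed PD event" and "Subjects without documented PD/death will be censored at the last disease assessment date". Neither mentions new therapy.

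Table 14 then gives:
- **Row 1** (no PD, no death, no new therapy): the primary analysis censors at the last assessment.
- **Row 2** (no PD, no death, new therapy started): primary, "Censored at last disease assessment before new anticancer treatment". Sensitivity Analysis 2 makes the new-therapy date an event.
- **Rows 3 and 4** (PD or death after at most one, or at least two, missed assessments): primary, "Progressed at date of documented PD or death" in both. Neither row has a condition on new therapy.

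The text on Sensitivity Analysis 2 takes treatment discontinuation or new therapy "to be a PD event for subjects without documented PD or death".

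On what is collected after a switch, section 5.8 takes subjects given non-protocol myeloma therapy before progression off study treatment; "however, tumor assessments must continue at 4 week intervals until documented progression". The closing paragraph of the same section says that subjects who discontinue for reasons other than progression "will have post-treatment follow-up for disease status until disease progression, initiating a non-study cancer treatment", among other end points. Section 7.1.2.8.5 also ends assessments at new treatment, as do sections 5.5.2, 7.1.1.5.5 and 7.1.5.5 for subjects in post-treatment follow-up. Section 7.1.5.5.1 continues to collect deaths.

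**The concern.** A censoring rule should use only what is known at the time of censoring. Here two subjects with the same history up to the switch are handled differently according to a later outcome. The one who stays event-free loses all time after the switch, and the one who progresses or dies keeps it. That is neither censoring at the switch for everyone nor following everyone regardless of new therapy.

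If the arms switch at different rates, the arm with more switching loses more event-free time and its hazard is overstated. PFS carries 1.5% of the 2.5% one-sided alpha. The situation is foreseeable, because the July 2017 clinical hold stopped study treatment in all subjects whether or not they had progressed.

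**Working it through.** **1. The plan's own figures reproduce (section 8.9 and Table 17).** Inputs: 300 subjects 1:1, 236 events, HR 0.635, one-sided alpha 1.5% (z = 2.170), control median 4 months, 14 months' accrual plus 6 months' follow-up, 5% yearly dropout.
- Power: √236/2 × |ln 0.635| − 2.170 = 7.681 × 0.454 − 2.170 = 1.32, which gives 90.6% (stated 90.6%).
- Bound: exp(−2 × 2.170/√236) = 0.754 (stated 0.75).
- Expected events at month 20: about 127.8 control + 108.1 pembrolizumab = 235.9 (stated about 236).

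**2. The table as a decision rule.** X and Y both start new therapy at month 3 without PD. X is alive without PD at cut-off. Y dies at month 10.

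| Rule | X | Y |
|---|---|---|
| Table 14, primary | censored by month 3 | event, month 10 |
| Censor at switch | censored by month 3 | censored by month 3 |
| Count PD or death regardless of new therapy, assessments continuing | followed past month 3 | event, month 10 |
| Table 14, Sensitivity Analysis 2 | event, month 3 | event, month 10 |

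Under Sensitivity Analysis 2 the subject who dies gets the longer PFS time. If assessments continue after month 3, the text of 8.6.1 censors X later than row 2 does. If they stop, the two dates coincide.

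**3. Size if only deaths are recorded after the switch.** Simulation with the design inputs above: 28-day visits, Efron ties, cut at 236 events, 2,000 trials per scenario. Assumed, because the documents give no values: switching shares, median survival of 9 months after the switch, and 10% of first events being deaths. With no switching the HR is 0.633.

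| Switching, control / pembrolizumab | Present rule | Censor at switch | Post-switch deaths among 236 events |
|---|---|---|---|
| 10% / 10% | 0.638 | 0.631 | 12 |
| 14% / 18% | 0.649 | 0.631 | 21 |
| 10% / 32% (stress) | 0.689 | 0.642 | 28 |
| 30% / 10% (stress) | 0.618 | 0.616 | 30 |

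The standard error of log HR is 2/√236 = 0.130. The first two differences are ln(0.638/0.631) = 0.011 and ln(0.649/0.631) = 0.028, or about 0.1 and 0.2 standard errors. The 10%/32% stress case is ln(0.689/0.642) = 0.071, about 0.5 standard errors.

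**4. Size if post-switch PD is also recorded.** Simulation cut at month 20, PFS hazard unchanged by switching, true HR 1, nominal rejection 1.5%:
- Equal switching: HR about 1.00 under all three rules.
- 10% pembrolizumab / 30% control: present rule HR 0.94, rejection 4.9%. Repeat runs gave 0.93 and 5.3% to 5.8%. Censor at switch gave 1.01 and 1.7%; counting PD or death regardless of new therapy gave 1.01 and 1.3%.
- 15% / 25%: present rule 0.97 and 2.8%; either single rule 1.4% to 1.5%.
- 30% / 10%: present rule 1.08 and 0.2%; either single rule 1.00.

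With deaths only in the same set-up, the null HR was 0.99 to 1.01 and rejection 1.0% to 2.9% (simulation error about 0.3 points near 1.5%).

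**The case against.** - **Every subject has a row.** Read literally, each subject falls in exactly one row, and counting every death is stated consistently in sections 8.4.1 and 8.6.1. This stands: a reader might infer that PFS has no defined rule for these subjects, and the documents do not support that. The defect is that the defined rule looks ahead. Reading row 2 as status at the switch does not help, because a later death then fits two rows and no precedence is given.
- **The effect is small.** This stands for moderate or equal switching. The large shifts need strongly unequal rates, which no passage supports.
- **The conflict over assessments is narrow.** Largely right. Sections 5.5.2, 7.1.1.5.5 and 7.1.5.5 can be read as covering post-treatment follow-up only. The direct overlap is between the bullet in 5.8, that section's own closing paragraph, and 7.1.2.8.5.
- **Sensitivity Analysis 1 already helps.** In part. It gives 0.631 and 0.635 in the first two cases of step 3, but only if visits not made after the switch count as missed, which the plan does not say.
- **Censoring everyone at the switch is no clear improvement as the primary.** This stands. It costs events and assumes that switching is unrelated to imminent PD. With 25% of switches falling in the month before PD, present rule against censor-at-switch is 0.642 v 0.625 (14% control/18% pembrolizumab) and 0.650 v 0.606 (10%/32%). With 50% it is 0.635 v 0.618 and 0.612 v 0.568. Against 0.633, censor-at-switch is further off in three of the four and about level in one.
- **The hold overtakes the planned cut.** Section 8.0 says the analysis may be modified and reported in the study report. That gives a route for the correction but does not make it.

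**Conclusion.** Wrong as written; minor to moderate. The dependence on later outcome follows from the wording alone. Its size rests on assumed switching rates and on which data exist after the switch. There is no null bias with equal switching, and a shift of about 0.1 to 0.2 standard errors in moderate deaths-only cases. The error rate is materially affected only when switching is strongly unequal and post-switch PD is recorded.

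Three stronger readings are not supported. A reader might infer that the PFS result is biased in a known direction, but direction follows the unknown difference in switching. A reader might infer that the power, event count or HR bound is wrong, but all three reproduce. A reader might infer that the primary must become censor-at-switch, but that rule has its own bias and cost.

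Sensitivity Analysis 2 shares the form of the problem. Its effect differs, because every event-free switcher becomes an event, and it was not simulated as written, so no size is claimed. The documents do not say how many subjects switched without PD, or whether the PFS cut-off preceded the hold.

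**What to change.** 1. Keep the primary as sections 8.4.1 and 8.6.1 state it: count PD or death regardless of new therapy. Change row 2 of the primary column to match row 1, so that assessments made after the switch are used.
2. That change does nothing for subjects whose assessments stopped at the switch. Add a pre-specified sensitivity analysis that censors every subject who starts new therapy without PD at the last assessment before it, whatever happens later. Report both, and state that the second assumes switching is unrelated to imminent PD.
3. In Sensitivity Analysis 2, use the new-therapy date for every subject who starts it without PD.
4. Reconcile the bullet in section 5.8 with that section's closing paragraph and 7.1.2.8.5, and with 5.5.2, 7.1.1.5.5 and 7.1.5.5 where they overlap. State which practice applied to the data collected.
5. Document the change by amendment or in the study report, as section 8.0 provides. Because the trial is open-label, give the date and say whether PFS by arm had been seen.

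Cost: a little programming and one more sensitivity analysis with about 12 to 30 fewer of 236 events under the assumed rates. By the formula in step 1, power at HR 0.635 for that analysis would be 89.0% with 224 events or 86.2% with 206. The primary event trigger is unchanged.
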